#### **Efficacy:**

(revised per Amendment 02)

• To demonstrate that, in obese and overweight subjects with CV disease and/or multiple CV risk factors, lorcaserin HCl 10 mg BID reduces the incidence of MACE+ (MACE or hospitalization for unstable angina or heart failure (HF), or any coronary revascularization) compared to placebo

#### 3.2 SECONDARY OBJECTIVES

## **Key Secondary Objective:**

• To confirm that, in subjects with pre-diabetes at Baseline based on 2013ADA guideline, lorcaserin HCl 10 mg BID reduces the incidence of conversion to type 2 diabetes mellitus (T2DM) compared to placebo (revised per Amendments 01 and 02)

#### Other Secondary Objectives (revised per Amendment 02)

## MACE and MACE+ Related: (revised per Amendment 02)

- To determine whether the rates of the individual events comprising the MACE+ endpoints are different in subjects on lorcaserin compared to those on placebo
- To determine whether lorcaserin reduces all-cause mortality compared with placebo

## Diabetes and Prediabetes Related: (revised per Amendment 02)

- To evaluate the effect of lorcaserin HCl 10 mg BID compared to placebo on conversion to normal glucose homeostasis at 1 year and yearly thereafter in subjects with prediabetes at Baseline (revised per Amendment 01)
- To evaluate whether in all subjects without any type of diabetes at Baseline, lorcaserin HCl 10 mg BID reduces the incidence of conversion to T2DM compared to placebo (revised per Amendment 01)
- To confirm that, in subjects with T2DM at Baseline, lorcaserin HCl 10 mg BID improves glycemic control (HbA1c) compared to placebo at 6 months

## **Renal Related: (revised per Amendment 02)**

- To evaluate the long-term effect of lorcaserin HCl compared to placebo on renal function in all subjects
- To evaluate the long-term effect of lorcaserin HCl compared to placebo on renal function in subjects with T2DM at Baseline
- To evaluate the long-term effect of lorcaserin HCl compared to placebo on renal function in subjects with prediabetes at Baseline (revised per Amendments 01 and 02)

## **Safety Objectives:** (revised per Amendment 02)

- To evaluate echocardiographically determined cardiac valvular function and pulmonary arterial pressure changes associated with treatment with lorcaserin HCl 10 mg BID compared to placebo at 1 year
- To evaluate the long-term safety of lorcaserin HCl 10 mg BID

## 3.2.1 Exploratory Objectives

• To explore the effects of long-term treatment with lorcaserin HCl 10 mg BID on improving CV risk factors associated with obesity (eg, body weight, dyslipidemia, insulin

- level, hypertension, inflammatory biomarkers) compared with placebo at 1 year and yearly thereafter
- To evaluate the effect of BELVIQ (lorcaserin HCl) on other diabetes-related microvascular complications (retinopathy and neuropathy compared to placebo in subjects with prediabetes, or T2DM at Baseline at EOS. (revised per Amendment 01)
- To explore, in subjects with a diagnosis of Non-Alcoholic Fatty Liver Disease (NAFLD) at Baseline, the effects of long-term treatment with lorcaserin HCl 10 mg BID on liver function compared with placebo at 1 year and yearly thereafter
- To evaluate echocardiographically determined heart valve and pulmonary artery pressure changes associated with treatment with lorcaserin HCl 10 mg BID compared to placebo at 2 years and yearly thereafter
- To collect and store DNA samples which may be used for examination of the impact of genetic variation on weight loss, the response to lorcaserin HCl, susceptibility to diabetes, and the risk of developing CV and other end-organ disease and their associated risk factors (for participating countries/sites where ethics and regulatory approval is obtained)
- To collect and store serum and plasma biomarker samples which may be used for examination of the impact of different metabolic and CV pathologic processes on weight loss, the response to lorcaserin HCl, susceptibility to diabetes, and the risk of developing CV and other end-organ disease and their associated risk factors (for participating countries/sites where ethics and regulatory approval is obtained)
- To explore the effects of long-term treatment with lorcaserin HCl (10 mg BID) on improvement of obesity related complications, as defined by the 2014 Advanced Framework for a New Diagnosis of Obesity as a Chronic Disease (American Association of Clinical Endocrinologists [AACE] and American College of Endocrinology [ACE]) (eg, pre diabetes, metabolic syndrome, hypertriglyceridemia/dyslipidemia, and potentially others) (revised per Amendment 01)
- To demonstrate that lorcaserin HCl 10 mg BID improves glycemic control, and/or reduction in OAD medications for the subjects treated with OADs, compared to placebo at 6 months in the following subpopulations of patients with T2DM:
  - o Subjects with T2DM with an HbA1c>7% at Baseline
  - o Subjects with T2DM who have not been treated with antidiabetic agents at Baseline
  - Subjects with T2DM who are on Monotherapy with an oral antidiabetic agent at Baseline
  - Subjects with early T2DM (duration of diagnosis of diabetes is less than 5 years) at Baseline

## 3.3 OVERALL STUDY DESIGN AND PLAN

This will be a multicenter, randomized, double-blind, placebo-controlled, parallel-group study in overweight and obese subjects with CV disease and/or multiple CV risk factors. Approximately 12,000 subjects will be randomized to 2 treatment groups in a ratio of 1:1, stratified by the presence of established CV disease (~80%) or CV risk factors without established CV disease

(~20%). The 80% of subjects in the established CV disease strata will consist of a group with T2DM (approximately 30% of the total number of subjects in the study) and a group without T2DM (approximately 50% of the total number of subjects in the study). The 20% of subjects in the strata with CV risk factors but without established CV disease will all have T2DM, as well as additional risk factors. Therefore, approximately 50% of the total number of subjects in the study will have T2DM (Table 1).

**Table 1 Approximate Stratification of Subjects** 

	CV Disease	CV Disease Risk	Total
T2DM	30%	20%	50%
No T2DM	50%	0%	50%
Total	80%	20%	100%

CV = cardiovascular, T2DM = type 2 diabetes mellitus.

The study will consist of 2 phases: Prerandomization and Randomization. The Prerandomization Phase will last up to 30 days and consist of 1 visit during which subjects will be screened for eligibility. The Randomization Phase will consist of 2 periods: Treatment and Follow-up. The Treatment Period will last for approximately 5 years with approximately 18 visits. The first dose should be taken at Visit 2. (revised per Amendment 01). The Follow-up Period extends from the end of treatment (EOT) visit to the EOS visit. Sponsor Notification of Study Completion will occur once, 1401 MACE+ events, 460 MACE events, and median treatment duration of 2.5 years occur. (revised per Amendment 02). This is expected to occur on or before October 2018. Following this announcement ("Sponsor Notification of Study Completion"), sites will be instructed to bring subjects who remain on treatment for an EOT visit. An EOS visit will occur approximately 30 days later for subjects on treatment at Sponsor Notification of Study Completion. (revised per Amendment 01). Subjects who are still being followed in the study but have already discontinued study medication  $\geq$  30 days before will return for an EOS visit. Subjects who are still being followed in the study but who discontinued study medication within the last 30 days will return for an EOS visit approximately 30 days after their last dose of study medication.

[figure not shown]
Subjects will receive lorcaserin HCl 10 mg BID or placebo BID for approximately 5 years. Throughout the duration of the study, subjects will be provided with instructions regarding a reduced-calorie diet and increased physical activity program (see Appendix 4 of the protocol). Echocardiography will be performed on a subset of subjects at Baseline and at 6, 12, 18, and 24 months, and yearly thereafter. Acquisition of new ECHO data in all subjects will cease when at least 1000 subjects have completed the Month 36 echocardiographic assessment.

All subjects will continue in the study until study completion, rather than for a prespecified number of visits. Subjects who prematurely discontinue study drug will continue in the study for all subsequent study visits until study completion and are to complete visit procedures as indicated in Table 4 in the protocol. It is preferred that these visits are in person. However, if the subject is unable to attend a visit in person, a telephone visit may be performed. The

outcome of the telephone visit must be clearly documented in the source record. At a minimum, the site should attempt to have the subject return for an in-person visit at least once per year. The study will terminate when 1401 MACE+ events have occurred and when there has been a median treatment duration of 2.5 years have accrued. (revised per Amendment 02) This is expected to occur on or before October 2018.

When 460 adjudicated MACE events have occurred, an interim analysis will be conducted on MACE events (see Section 6). It will be conducted to establish whether the primary safety objective (MACE noninferiority) has been achieved. This analysis will be performed by an independent statistician and governed by an independent Data Monitoring Committee (DMC) and is anticipated to occur on or before (approximately) July 2017. If the primary safety objective has been achieved, the trial will continue for evaluation of additional endpoints as delineated in the objectives.

An overview of the study design is presented in Figure 1.

**Figure 1 Study Design Schematic** BID = twice daily; EOS = end of study; EOT = end of treatment; R = randomization.

#### 3.3.1 Prerandomization Phase

The Prerandomization Phase will last up to 30 days and consist of 1 visit during which subjects will be screened for eligibility and continue until randomization or exclusion. The purpose of the Prerandomization Phase is to obtain informed consent and to establish protocol eligibility. Informed consent will be obtained after the study has been fully explained to each subject and

before the conduct of any screening procedures or assessments. Procedures to be followed when obtaining informed consent are detailed in Section 5.3 of the protocol.

Subjects must be overweight or obese with CV disease or other CV risk factors and must meet all inclusion and exclusion criteria. The Screening Disposition case report form (CRF) page must be completed to indicate whether the subject is eligible to participate in the study and to provide reasons for screen failure, if applicable.

#### 3.3.2 Randomization Phase

The duration of the Randomization Phase will be approximately 56 months and will include 2 periods: Treatment and Follow-up. Subjects whose screening assessments and evaluations are completed and reviewed by the investigator and who continue to meet all of the inclusion/exclusion criteria will enter the Randomization Phase. Subjects will be randomized in a 1:1 ratio to receive lorcaserin HCl 10 mg BID or placebo.

#### 3.3.2.1 Treatment Period

The Treatment Period will last for approximately 5 years with approximately 18 visits. The first dose should be taken at the Randomization visit (Visit 2). (revised per Amendment 01) During the Treatment Period, subjects will continue treatment with the dose of lorcaserin HCl 10 mg or placebo BID in blinded fashion.

## 3.3.2.2 Follow-up Period

For subjects who remain in the study through the Sponsor Notification of Study Completion, the Follow-up Period will begin immediately after the EOT assessments have been completed, and will consist of 1 EOS visit, occurring 30 days + 10 days after last dose of study drug for subjects who complete study treatment. (revised per Amendments 01 and 02) See Section 9.3.3 of the protocol for procedures for subjects who prematurely discontinue study drug.

The scheduled of assessments are presented in Table 4 of the protocol.

#### 4 DETERMINATION OF SAMPLE SIZE

A sample size of 12,000 subjects should provide the required power for the primary endpoints and key secondary endpoint as follows:

### **Primary Endpoints (revised per Amendment 02)**

- For 460 MACE events to have occurred by approximately 43 months from start of the trial, providing 95% power to exclude a noninferiority margin of 1.4, assuming an annual background rate of 1.5%, 15-month accrual period, 5% annual drop-out rate,  $\alpha = 0.025$ , and a 1-sided test
- For 1401 MACE+ events to have occurred by approximately 54 months from the start of the trial, providing > 85% power to detect a 15% risk reduction with loreaserin HCl, assuming an annual background rate of 3.5%, 15-month accrual period, 5% annual dropout rate,  $\alpha = 0.05$ , and a 2-sided test

#### **Key Secondary Endpoint (revised per Amendment 02)**

• For 457 events of conversion to T2DM in subjects who are prediabetic at the time of enrollment ( $\sim$ 33%) to have occurred by approximately 54 months from the start of the study, providing 86% power to detect a 25% risk reduction with lorcaserin HCl, assuming an annual background rate of 4%, 15-month accrual period, 5% annual dropout rate,  $\alpha = 0.05$  and a 2-sided test.

#### 5 STATISTICAL METHODS

Statistical analyses will be performed by the sponsor or designee after the study is completed and the database is locked and released for unblinding. Statistical analyses will be performed using SAS software or other validated statistical software as required.

All descriptive statistics for continuous variables will be reported using mean, standard deviation (SD), median, minimum and maximum. Categorical variables will be summarized as number (percentage) of subjects.

#### 5.1 STUDY ENDPOINTS

Time from randomization to first occurrence of MACE will be the only endpoint to be analyzed at the Interim Analysis. All other endpoints will be analyzed at Study Completion.

## **5.1.1 Primary Endpoints**

- Time from randomization to first occurrence of MACE (first occurrence of any of the following events: MI, stroke, or CV death) at Interim Analysis only.
- Time from randomization to first occurrence of MACE+ (first occurrence of any of the following events: MACE or hospitalization for unstable angina or HF, or any coronary revascularization)

## 5.1.2 Key Secondary Endpoint (revised per Amendment 02)

- Time from randomization to conversion to T2DM, defined as first occurrence of any component of the 2013 ADA diagnostic criteria in subjects with prediabetes at Baseline. The diagnostic criteria are met if a subject has unequivocal hyperglycemia (random plasma glucose ≥ 200 mg/dL (11.1 mmol/L) with classic symptoms of hyperglycemia or hyperglycemic crisis) OR any of the following criteria are observed and subsequently confirmed on repeat laboratory testing: (revised per Amendments 01 and 02):
  - $\circ$  HbA1c  $\geq$  6.5%
  - $\circ$  FPG  $\geq$  126 mg/dL (7.0 mmol/L)
  - o 2-hour plasma glucose ≥200mg/dL (11.1 mmol/L) by an OGTT

Investigators should make every effort to obtain central lab confirmatory testing no later than 6 weeks after meeting any of the above criteria. Abnormalities of any 1 of the above 3 criteria on repeat testing constitutes diagnostic confirmation of diabetes. Subjects who have been started on anti-diabetic medications following abnormalities in preliminary testing do not require confirmatory testing. (revised per Amendments 01 and 02).

## 5.1.3 Other Secondary Endpoints (revised per Amendment 02)

#### **MACE and MACE + Related: (revised per Amendment 02):**

- Time from randomization to first occurrence of each of the individual components of MACE+
- Time from randomization to first occurrence of all-cause mortality

## Diabetes and Prediabetes Related (revised per Amendment 02):

- Time from randomization to conversion to normal glucose homeostasis (HbA1c $\leq$ 5.6% and fasting plasma glucose <100 mg/dL without any antidiabetic treatment) in subjects with prediabetes at Baseline (revised per Amendments 01 and 02). ). See Section 8.3.2 for definition.
- Time from randomization to conversion to T2DM in subjects without any type of diabetes at Baseline. (revised per Amendment 01). See Section 8.3.1 for definition
- Change from Baseline in HbA1c at 6 months in subjects with T2DM at Baseline

## **Renal Related (revised per Amendment 02)**

- Time from randomization to first occurrence of 2 consecutive assessments within the same component of the composite endpoint or time to first occurrence of renal transplant or renal death, on scheduled or nonscheduled visits at least 30 days apart, indicative of new onset renal impairment or worsening of existing renal impairment (first occurrence of any of the following events: microalbuminuria, macroalbuminuria, worsening albuminuria, newly developed CKD or worsening of CKD, or doubling of serum creatinine, as defined above, or any of the following: ESRD, renal transplant, renal death) in all subjects. (revised per Amendment 02). See Section 8.2.1 for definitions.
- Time from randomization to first occurrence of 2 consecutive assessments within the same component of the composite endpoint or time to first occurrence of renal transplant or renal death, on scheduled or non-scheduled visits at least 30 days apart, indicative of new onset renal impairment or worsening of existing renal impairment (first occurrence of any of the following events: microalbuminuria, macroalbuminuria, worsening albuminuria, newly developed CKD or worsening of CKD, or doubling of serum creatinine, as defined above, or any of the following: ESRD, renal transplant, renal death) in subjects with prediabetes at Baseline (revised per Amendments 01 and 02). See Section 8.2.1 for definitions

- Time from randomization to first occurrence of 2 consecutive assessments within the same component of the composite endpoint or time to first occurrence of renal transplant or renal death, on scheduled or nonscheduled visits at least 30 days apart, indicative of new onset renal impairment or worsening of existing renal impairment (first occurrence of any of the following events: microalbuminuria, macroalbuminuria, worsening albuminuria, newly developed CKD or worsening of CKD, or doubling of serum creatinine, as defined above, or any of the following: ESRD, renal transplant, renal death) in subjects with T2DM at Baseline (revised per Amendment 01). (revised per Amendment 02). See Section 8.2.1 for definitions
- Time from randomization to first occurrence of 2 consecutive assessments, on scheduled or nonscheduled visits at least 30 days apart, indicative of improvement in renal function (first occurrence of regression of albuminuria or regression of CKD) in subjects with T2DM at Baseline. See Section 8.2.2 for definitions

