9.5.1.4 Pharmacokinetic, Pharmacodynamic, and Pharmacogenomic/Pharmacogenetic Assessments

PHARMACOKINETIC ASSESSMENTS

Not applicable

PHARMACODYNAMIC ASSESSMENTS

The following will be measured for assessment of CV risk factors:

1. SBP, DBP, heart rate (HR)
2. Triglycerides, total cholesterol, HDL-C, LDL-C
3. FPG, fasting insulin

The following parameters related to renal function will be assessed.

- Urinary ACR

- ACR will be measured in spot urine.
- The following are the definitions of newly developed, worsening, and regression of albuminuria which need to be documented in 2 consecutive scheduled or nonscheduled assessments at least 30 days apart:
 - Newly developed albuminuria, defined as first evidence of microalbuminuria (ACR ≥ 30 $\mu\text{g}/\text{mg}$ in spot urine) **or** macroalbuminuria (ACR ≥ 300 $\mu\text{g}/\text{mg}$),¹¹ and ACR value increases $\geq 30\%$ from previous assessment during treatment
 - Worsening albuminuria, defined as when subjects with microalbuminuria at Baseline develop macroalbuminuria, and ACR value increases $\geq 30\%$ from previous assessment during treatment
 - Regression of albuminuria, defined as when subjects with macroalbuminuria at Baseline develop microalbuminuria or non-albuminuria, or subjects with microalbuminuria at Baseline become non-albuminuric, and ACR value decreases $\geq 30\%$ from previous assessment during treatment

- Estimated glomerular filtration rate (eGFR):
 - eGFR will be calculated by the CKD-EPI equation based on creatinine measurement in the total population and/or cystatin C measurement in a selected population. The full criteria for determining whether creatinine, cystatin C, or an algorithm incorporating both will be used to estimate GFR will be detailed in the statistical analysis plan (SAP).
 - Definitions for newly developed, worsening, and regression of chronic kidney disease (CKD)¹² (see [Appendix 2](#)) in the absence of acute, transient, kidney injury
 - Newly developed CKD, defined as when a subject with eGFR ≥ 90 mL/min per 1.73 body surface area (BSA) and without kidney damage at Baseline changes to CKD Stage 1 or higher classified by the 2002 National Kidney Foundation (NKF) guidelines, where kidney damage referred to in the guideline is defined as the emergence of microalbuminuria as defined above, during treatment

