#### 8.2 DETERMINATION OF RENAL IMPAIRMENT OR IMPROVEMENT

### 8.2.1 Determination of new onset or worsening of Renal Impairment

Time from randomization to first occurrence of 2 consecutive assessments within the same component of the composite endpoint or time to first occurrence of renal transplant or renal death, on scheduled or nonscheduled visits at least 30 days apart, indicative of new onset renal impairment or worsening of existing renal impairment (first occurrence of any of the following events: microalbuminuria, macroalbuminuria, worsening albuminuria, newly developed CKD or worsening of CKD, or doubling of serum creatinine, or any of the following: ESRD, renal transplant, renal death). Table 4 presents the definitions for each of these events and Appendix 13.2 presents the definition of Chronic Kidney Disease (CKD) stages.

Table 4 Definitions of new	1 1 1	• •	1
Lobio / Hotinitions of nov	IN CONDON OF	WARRANINA AT RANG	I impoirment avents
Table 4 Delillions of new	iv develon or	WOLSEILING OF LEUX	i illiliali illelli evellis
THE I Delimitions of her	i, action or	" or seming or rema	

Renal Impairment Event	Definition
Newly Developed Albuminuria	For subjects without any microalbuminuria (ACR ≥ 30 μg/mg in spot urine), or macroalbuminuria(ACR ≥ 300 μg/mg in spot urine) at baseline or subject shows first evidence of;  • microalbuminuria (ACR ≥ 30 μg/mg in spot urine) with an ACR value increased ≥ 30% from Baseline  or  • macroalbuminuria(ACR ≥ 300 μg/mg in spot urine) with an ACR value increased ≥ 30% from Baseline
Worsening albuminuria	microalbuminuria present at Baseline and develops macroalbuminuria, and ACR value increases ≥30% from baseline assessment during treatment
Newly develop CKD	eGFR ≥ 90 mL/min per 1.73 body surface area (BSA) and without kidney damage at Baseline changes to CKD Stage 1 or higher classified by the 2002 National Kidney Foundation (NKF) guidelines, where kidney damage referred to in the guideline is defined as the emergence of microalbuminuria as defined above, during treatment
Worsening of CKD	CKD Stage 1 or higher defined by NKF guidelines worsens to higher CKD stages (eGFR ≥ 90 with albuminuria at Baseline decreases to < 90, or eGFR 60 to 89 at Baseline becomes <60, or eGFR 30 to 59 at Baseline becomes < 30 mL/min per 1.73 BSA) during treatment
Doubling of serum creatinine	creatinine value is at least 2 times the Baseline value and ≥ 1.5mg/dL during treatment

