### 8.2.2 Determination of Improvement of Renal function

Time from randomization to first occurrence of 2 consecutive assessments, on scheduled or nonscheduled visits at least 30 days apart, indicative of improvement in renal function (first occurrence of regression of albuminuria or regression of CKD), see Appendix 13.2 for definitions CKD stages. The renal improvement events are defined as;

Regression of albuminuria: defined as when subjects with macroalbuminuria at Baseline develop microalbuminuria or non-albuminuria (ACR < 30  $\mu$ g/mg in spot urine), or subjects with microalbuminuria at Baseline become non-albuminuric, and ACR value decreases  $\geq$  30% from previous assessment during treatment.

Regression of CKD: defined as when a subject with CKD Stage 1 or higher at Baseline improves to normal or lower stages by NKF guideline (eGFR  $\geq$  90 with albuminuria at

Baseline improves to eGFR  $\geq$  90 without albuminuria (ACR < 30 µg/mg in spot urine), or eGFR 60 to 89 at Baseline becomes eGFR  $\geq$  90 with or without albuminuria, or eGFR between 30 to 59 at Baseline improves to > 60 mL/min per 1.73 BSA) during treatment.

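### Renal improvement is defined less strictly than renal worsening in two places, so small ACR changes around 30 µg/mg can count as improvement

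*SAP*

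**What the plan says.** **Endpoint.** The last renal bullet in SAP 5.1.3 is a time to event "indicative of improvement in renal function (first occurrence of regression of albuminuria or regression of CKD) in subjects with T2DM at Baseline".

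**Confirmation.** Each of the three worsening bullets in SAP 5.1.3 (Renal Related) asks for "2 consecutive assessments within the same component of the composite endpoint". The improvement bullet asks only for "2 consecutive assessments, on scheduled or nonscheduled visits at least 30 days apart, indicative of improvement in renal function". SAP 8.2.2 repeats that shorter form, as does the improvement endpoint in protocol 9.7.1.1.

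Protocol 9.5.1.4 adds a separate condition for the albuminuria events: new onset, worsening and "regression of albuminuria which need to be documented in 2 consecutive scheduled or nonscheduled assessments at least 30 days apart". SAP 8.2.2 does not carry this condition over, and neither document has an equivalent for regression of CKD.

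**Size of change.** Under SAP 8.2.2, regression of albuminuria needs a lower ACR category plus a 30% fall; the relevant branch reads "subjects with microalbuminuria at Baseline become non-albuminuric, and ACR value decreases" and takes the fall from the previous assessment. Regression of CKD from Stage 1 needs only eGFR still at or above 90 and ACR below 30. Either event suffices for the endpoint.

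In the opposite direction, SAP Table 4 defines newly developed CKD by reference to "kidney damage referred to in the guideline is defined as the emergence of microalbuminuria as defined above". The entry above it in that table, newly developed albuminuria, requires a rise of at least 30% from Baseline.

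**The concern.** The plan treats a bare crossing of the ACR 30 line as insufficient evidence of regression of albuminuria, yet accepts the same crossing as regression of CKD in a Stage 1 subject. Because the endpoint is met by either component, the weaker rule decides for subjects just above the line. The missing same-component wording could also let one isolated ACR reading and one isolated eGFR reading confirm each other.

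At stake is what the reported improved proportion and its hazard ratio mean in the T2DM set. Events that reflect only measurement variation dilute the contrast between arms, and improvement cannot be set directly against worsening if the two were held to different standards.

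**Working it through.** The documents give no event count, power or sample size for this endpoint, so there is no stated figure to reproduce.

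**1. One subject, two rules.** Stage 1, Baseline ACR 31, then 29 and 29. The fall is (31 − 29)/31 = 6.5%. Regression of albuminuria: not met (30% needed). Regression of CKD: met. Endpoint: event. This needs no assumption.

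**2. Where the missing rule can matter.** If Baseline is *b* and a later value is below 30, the fall exceeds 1 − 30/*b*. That reaches 30% once *b* ≥ 30/0.7 = 42.9. So, measured against Baseline, the absent rule changes the outcome only for *b* between 30 and 42.9 µg/mg.

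**3. Stable subjects at a fixed ACR.** True value equal to Baseline, four follow-up readings, assumed CV 30%, event = two consecutive qualifying readings:

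| ACR | Counted as written | With 30% fall from Baseline |
|---|---|---|
| 31 | 43.5% | 3.5% |
| 35 | 21.6% | 3.6% |
| 40 | 7.2% | 3.5% |
| 50 | 0.5% | 0.5% |

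**4. The Stage 1 albuminuric group.** Assumptions, none given in the documents: true ACR lognormal with median 30 and log-SD 1.1; lognormal error; one Baseline reading between 30 and 299; five later readings; eGFR staying at or above 90.

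| Assumed CV | No true change: as written | No true change: 30% fall from Baseline | True ACR halves: as written | True ACR halves: 30% fall from Baseline |
|---|---|---|---|---|
| 30% | 12% | 7% | 52% | 50% |
| 40% | 16% | 12% | 53% | 51% |
| 60% | 22% | 19% | 55% | 53% |

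About a quarter of this simulated group has Baseline ACR 30 to 42.9. Within that quarter, noise-only events are roughly 36 to 46% as written and 18 to 35% with the rule. Other assumptions (log-SD 1.0, medians 15 to 60, CV 30 to 70%, four readings) give 6.0 to 35.5% as written and 3.5 to 32.0% with the rule.

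**5. The reference point.** SAP 8.2.2 measures the albuminuria fall from the previous assessment, while Table 4 measures the rise from Baseline. If the 8.2.2 form were placed in the Stage 1 branch and both confirming readings had to meet it, a sustained true halving would be detected only 6 to 14% of the time, because a value that has already dropped does not drop a further 30% at the next visit.

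**6. Mixed-component pairs.** Stage 2 subjects with microalbuminuria, true eGFR mean 80 and SD 15, eGFR CV 5 to 12%, ACR CV 30 to 70% (all assumed): noise-only events run from 13.6 to 35.6% with any pair and from 12.9 to 32.2% with same-component pairs, a difference of about 1 to 3 points.

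**7. Effect on the hazard ratio.** As a rough guide, if 20% of events are noise and the true ratio is 1.25, the observed ratio is near 0.8 × 1.25 + 0.2 = 1.20.

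**The case against.** Five points deserve weight.

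- A reader might infer that nothing stops an ACR fall at one visit and an eGFR rise at the next from confirming each other. Protocol 9.5.1.4 does not support that inference: it requires regression of albuminuria itself to be documented twice. What stands is narrower. The SAP omits the sentence, and regression of CKD has no such condition in either document.
- A reader might infer that every Stage 1 subject escapes the 30% rule. Step 2 shows that, against Baseline, the rule makes no difference above 42.9. A Stage 1 subject moving from macro- to microalbuminuria still has albuminuria, so the CKD branch is not met and the 30% rule applies.
- The worsening endpoint is not protected throughout. Worsening of CKD has no minimum eGFR change, and the 30% rise in newly developed CKD depends on reading the cross-reference in "where kidney damage referred to in the guideline is defined as the emergence of microalbuminuria as defined above, during treatment" as including it. That is the natural reading but not an explicit one.
- Most noise events survive the change: about 60 to 88% of them in step 4. They come from the single Baseline value (SAP 8) and the fixed cut-off.
- The endpoint is supportive, outside the gatekeeping hierarchy (SAP 5.3.3 and 5.4.3), and SAP 5.8 also plans continuous eGFR and ACR models without cut-offs.

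All five limit the size of the problem. None removes the inconsistency in step 1.

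**Conclusion.** The point holds as a definitional inconsistency of modest size. Two facts rest on the text alone: the same-component wording is missing for improvement in the SAP, and a Stage 1 subject with Baseline ACR 30 to 42.9 can be counted as improved on a change that the albuminuria rule rejects.

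The percentages rest on assumed ACR and eGFR variability and an assumed ACR distribution. The share of the T2DM set that is Stage 1 with ACR in that range is not given, so the effect on the actual endpoint cannot be stated.

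A reader might infer that the looser definition could manufacture a treatment benefit. The documents do not support that: with blinded randomised arms the noise should fall on both alike, which pulls the hazard ratio toward 1 and raises the improved proportion in each arm. No confirmatory conclusion depends on it.

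**What to change.** Before unblinding, amend the SAP:

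- **5.1.3 and 8.2.2:** require both confirming assessments to be in the same component, as the worsening bullets do. This agrees with protocol 9.5.1.4 for albuminuria and extends it to regression of CKD.
- **8.2.2, Stage 1 branch of regression of CKD:** require an ACR fall of at least 30% from Baseline, not from the previous assessment (see step 5).
- **8.2.2, regression of albuminuria:** use the same Baseline reference, as Table 4 already does for worsening. Protocol 9.5.1.4 uses the previous assessment, so record the departure in SAP Section 7.

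Cost: wording and derivation code only, with no new data. Slightly fewer events would be counted; in the simulation, detection when true ACR halves drops by about 2 percentage points.
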